3.0 IMPLEMENTATION OF STUDY

3.1 STUDY DESIGN

3.1.1 RANDOMIZED DESIGN

This is a randomized, cross-over, double-blinded, placebo-controlled pediatric phase II trial of oral R115777 in children and young adults with NF1 who have progressive plexiform neurofibroma(s). Patients will be randomized to either receive R115777 or placebo first. After documentation of progressive disease on the first treatment, patients will be crossed over to receive R115777 (if placebo was first given) or placebo (if R115777 was first given). The first treatment that a patient is randomized to receive (either placebo or R115777) is defined as "phase A", and the second treatment (either placebo or R115777), is defined as "phase B". There should be a 2 week washout period, during which no drug is administered, when crossing over from the first (phase A) to the second (phase B) treatment. The treatment cycle number will reset to "1" when the patient crosses over from "phase A" to "phase B". For study purposes "arm 1" is defined as treatment with R115777 first followed by placebo, and "arm 2" is defined as treatment with placebo first followed by R115777.

3.1.2 PATIENT REGISTRATION AND RANDOMIZATION

Patients must be registered by contacting [name] at the Pediatric Oncology Branch (POB) (phone number, [contact], e-mail: [contact]). When registering a patient, information about all entry criteria (e.g., laboratory results) must be available to allow for verification of eligibility. [name] ([contact], e-mail: [contact]) or [name] (phone number 301-

[name], e-mail [contact]) must also be contacted to discuss the patient prior to entry on study. The completed Eligibility Checklist (Appendix 8A) and the Blinded Patient On Study Form (Appendix 8B) must be faxed to the (POB) c/o [name] ([contact]). All patients will be registered with Orkand ([contact], [contact]) by the POB research nurse. Orkand will notify the POB research nurse and the Pharmaceutical Management Branch (PMB), CTEP, NCI of the patient's ID number using the completed Blinded Patient On Study Form (Appendix 8B). The POB research nurse will notify the registering site of the patient's ID number and, based on notification by Orkand, the PMB will ship drug for that specific patient ID number to the registering site (see section 8.0). After patient registration the POB research nurse will also ship a module with the necessary materials to administer the quality of life assessment, and the required tests outlined in Appendix 5, 6, and 7 to the participating institution. The POB research nurse must also be notified when the patient progresses after "phase A" (i.e., crossover notification to the PMB) and when the patient progresses after "phase B" (i.e., off-study notification to Orkand and PMB) by faxing the completed Progression Checklist (Appendix 9A) and the Blinded Patient Crossover/Off Study Form (Appendix 9B) to the Pediatric Oncology Branch (c/o [name]) at [contact]. The POB research nurse will notify the PMB when a patient progresses on treatment "phase A", and Orkand and the PMB when a patient progresses on treatment "phase B" using the completed Blinded Patient Crossover/Off Study Form (Appendix 9B). A "roadmap" for the patient registration process is shown in Appendix 10.

3.1.3 Dosing Schedule and Prescribing

R115777 or placebo will be administered orally q12h for 21 days followed by a 7 day rest period between cycles (28-day treatment cycle). The patient's prescriptions must include the patient ID number (e.g., 01C0222-01), the patient initials (e.g. ABC = first three letters of patient's last name), the phase (i.e., "Phase A" or "Phase B"), the **body surface area** (in m²), and the dose (i.e. mg po q12h). "Phase A" will be defined as the treatment after initial randomization until documentation of progressive disease. "Phase B" will be defined as the treatment after the patient is crossed over to receive R115777 (if placebo was first given) or placebo (if R115777 was first given). The dosage of R115777 will be 200 mg/m²/dose (see dosing table in section 3.2). Patients will continue on therapy until they meet one of the off-study criteria (Section 3.6). There should be a 2 week washout period, during which no drug is administered, when crossing over from "Phase A" to "Phase B". Patients or their guardians will keep a diary to document the intake of each dose of R115777 and potential side effects (Appendix 11A). Each institutional pharmacy will ensure quality control procedures for R115777 and placebo allocation, and will use the Pill Count Case Report Form (Appendix 11B) for dispensing the boxes, and for counting the dispensed and returned tablets. The tearoff labels from boxes will also be attached on this form. The patient diary and the Pill Count Case Report Form should be reviewed with the patient's family after completion of every three treatment cycles, and drug should be accounted for at this

time (Appendix 11A/B). These diaries and copies of the Pill Count Case Report Form will be forwarded to [name] (Pediatric Oncology Branch, NCI, [contact], [contact]) after completion of every 3 treatment cycles.

3.1.4 MONITORING TIME TO PROGRESSION AND RESPONSE

This phase II trial is designed to determine the time to tumor progression and response rate with R115777 in patients with NF1 and progressive plexiform neurofibromas. The primary endpoint will be time to progression. Each patient will undergo MRI imaging of all known disease prior to entry on study. At the time of study entry one to three progressing plexiform neurofibroma(s) will be identified as index lesion(s), and followed for progression and response using 1D-, 2D-, and 3D-MRI. Results obtained with 1D-MRI and 3D-MRI analysis will be compared to conventional 2D-MRI analysis for their ease and reproducibility. The imaging protocol outlined in Appendix 1 will be used each time MRI scans are performed to assess response to R115777. MRI scans are performed prior to cycles 1, 4, 7, 10, and then after every 6 cycles on each study phase. If a patient is removed from a study phase because of clinical evidence of disease progression, the MRI scans should be repeated if they had not been performed within the past 4 weeks.

3.1.5 Definition of Tumor Progression

- A ≥ 20% increase in the volume (by 3D-MRI) of at least one of the index plexiform neurofibromas compared to the pretreatment volume measured prior to the start of the current treatment phase.
- Appearance of new discrete dermal neurofibroma(s) does not qualify for disease progression.
- Worsening of existing symptoms or the appearance of new symptoms that persist for more than 7 days and that are felt to be definitely related to plexiform neurofibroma should be evaluated by repeating the MRI. Patients should not be classified as having progressive disease solely on the basis of new or increased symptoms without discussing the case with the protocol Principal Investigator.
- Patients with other evidence of disease progression than outlined above should also be discussed with the Principal Investigator.

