The program then performs a histogram analysis of signal intensity pixel by pixel and a threshold that distinguishes high signal intensity tumor from normal tissue is defined (Figure 1C). Tumor contours are then determined using a gradient image, connected component analysis and automatic edge following operation (Figure 1D). There is an option for re-analysis of MR images using an average or selected threshold. Tumor volume is calculated by summing the results from all images based on the resulting 2-D contours and slice thickness; and a report is generated.

For comparison, plexiform neurofibroma volume was also determined by manually tracing the tumor borders on each MR image. The results of application of the automated method are shown in the table below.

	Observer 1	Observer 2
Mean tumor volume ml, median (range)	291 (80.9-1581)	290 (75.7-1603)
Inter-day CV %, median (range)	3.6 (0.7-6.0)	1.6 (0.6-5.6)
Median (range) % difference in volume between	6.4 (1.4	– 11 9)
observers	0.1 (1.1	11.7)
Correlation automated vs. manual method, R	0.999	0.999

This automated volumetric MRI analysis is applicable to most plexiform neurofibromas, has excellent intra- and inter-observer reproducibility and agrees with volumes determined by manual tumor tracing. This method is used in the currently ongoing phase II trial of the farnesyltransferase inhibitor R115777 and in the phase I trial of pirfenidone for children with NF1 and plexiform neurofibromas to assess changes in tumor size, and in both clinical trials tumor progression is defined as an increase in tumor volume by $\geq 20\%$.

This volume increase corresponds to much smaller changes in 1-D, or 2-D measurements as outlined in the table below.

Response Criteria	RECIST	WHO	Phase II R117555
	Diameter, 2r	Product, $(2r)^2$	Volume, $4/3$ Π r^3
Disease progression (Increase)	20	44	73
	12	25	40
	6	13	20

Shaded areas show current criteria used to define disease progression by RECIST, WHO, and the ongoing R115777 NF1 phase II trial

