Because the estimate of time to progression for patients eligible for this trial is approximately 6 months, it would be desirable to increase this time to 12 months. A one-tailed hypothesis will be used since it would only be considered interesting to see the improvement of drug compared to placebo. With 80% power and a one-tailed alpha=0.05, in order to detect a difference in median time to progression (during the first part of the trial) between the two arms of 6 vs. 12 months, 30 patients per arm are required (60 total) assuming 36 months of accrual and 12 months of additional follow-up following entry of the last patient. Kaplan-Meier analysis using log-rank statistics will be used to perform the required evaluation. We plan to replace patients who were diagnosed with a malignant peripheral nerve sheath tumor (MPNST) after enrolling on study, as these patients will not be evaluable for the primary outcome measure, which is time to progression of progressive plexiform neurofibromas. For this reason we will increase the accrual ceiling to 63 patients

Randomization of patients between the two study arms will be performed centrally by Orkand (See Section 3.1.1, 3.1.2). With more than one institution participating, it is expected that 20 patients per year can be entered onto the trial, with an expected accrual period of 3 years.

This trial will be monitored by the NCI/DCS Data Safety and Monitoring Board. Due to the projected accrual rate, it is expected that 3 interim evaluations and a final evaluation will take place at each of 4 consecutive annual meetings of the DSMB. Using the O'Brien-Fleming approach, if the p-values at the following evaluations are less than or equal to those tabled below, then the trial would be declared to have a statistically significant result; no further accrual would be required once such a determination has been made.

Evaluation #	Threshold p-Value (one-tailed)
1	0.00005

2	0.0039
3	0.0184
4 (FINAL)	0.0412

In addition, if, at any annual evaluation, a conditional power analysis indicates that there is a minimal chance of declaring a significant advantage to drug with the addition of the remaining planned patients based on results to date and the hypothesized results, then the DSMB may choose to close the study to further accrual.

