APPENDIX 8 A: ELIGIBILITY CHECKLIST FOR PROTOCOL

Patient initials:	First three letters of last name	e:
Date of birth:		
Patient measurements:	Weight (kg): Height (c	
(please average 3 heights and weights)		(m²):
Institution:	Ph	ıysician:
NF1 diagnostic criteria:	Plexiform neurofibroma:	≥6 Café-au-lait spots:
G	Freckling:	Optic glioma:
	≥ 2 Lisch nodules:	Bony dysplasia:
	1st degree relative with NF1:	
Progressive plexiform	≥20% increase in tumor volume: ≥13% increase in product of two	%:
Neurofibroma	longest perpendicular diameters:	%:
over prior two scans:	≥6% increase in longest diameter:	%:
	Date of scans: Tumor measurements:	1 2 cm: cm:
	Inoperable:	Yes: No:
	Measurable: Potential for morbidity:	res: No:
	Location:	
Recovered from tox. of prior Rx:	Yes: No:	
Date of last dose of (NA if none):	Radiation Rx:	ChemoRx:
ECOG performance score:	Life expectancy ≥12	mo: Yes: No:
	Date CBC/Diff and coags draw	vn:
Hematologic parameters:	ANC: Hgb:	Plt:
	Fibrinogen: N	Normal range:
	Date chemistries drawn: _	
Liver function tests:	SGPT: ULN:	Bili: ULN:
Renal function:	Creat: Normal range: _	or Creat clear:
Signed informed consent:	Yes: Date:	No:
Pregnant or breast feeding:	Yes: No: Date	e of pregnancy test:
Other significant illnesses:	Yes: No:DPA offered:	Yes: No: NA:
>1 myelosuppressive chemoRX:	Yes: No: Prior	r R115777: Yes No:
Investigational agent last 30 days:	Yes: No:	· — —
Active MPNST or other cancer	Yes: No:	
Ongoing XRT, chemoRX, GCSF, hormonal or immunoRx	Yes: No:	
Able to return for follow-up	Yes No:	
-	-	

Name of person completing form: _____ Signature/Date: _____

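### Progression in any one of up to three index lesions makes lesion count prognostic by construction, but the phase A log-rank test does not account for it

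*Combined protocol and SAP*

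**What the plan says.** Sections 2.2.7 and 3.1.4 and Appendix 1 have one to three progressing plexiform neurofibromas chosen as index lesions at entry. If more than three are progressing, the three most clinically relevant are followed. Sections 3.1.5 and 5.2 define progression as a volume increase of 20% or more "of at least one of the index plexiform neurofibromas compared to the pretreatment volume" at the start of the current phase.

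Section 5.4.2 takes the first treatment period as the primary comparison: "Kaplan-Meier analysis using log-rank statistics will be used to perform the required evaluation". The design is set "With 80% power and a one-tailed alpha=0.05", for median times to progression of 6 against 12 months with 30 patients per arm, "assuming 36 months of accrual and 12 months of additional follow-up following entry of the last patient". Randomisation is central, and no stratification factor is named for it or for the analysis. The only other variable mentioned is age, as an example, in connection with the paired first-versus-second-phase comparison. That comparison is additional to the primary test.

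**The concern.** If any one lesion can trigger the event, the patient's time to progression is a minimum over lesions. Unless lesions within a patient are perfectly correlated, that minimum falls as the count rises. This follows from the endpoint rule and needs no natural-history data. Measurement error works in the same direction, because each extra lesion is another chance for a reading to cross 20%.

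Two things are at stake in a 60-patient trial. First, pooling patients with different hazards pulls the marginal hazard ratio toward 1, so a log-rank test that ignores the factor has less power than one that uses it. Second, lesion count is fixed at baseline but not balanced by design, so an excess of multi-lesion patients in one arm shifts the observed difference directly.

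**Working it through.** **1. The plan's own figure.** Inputs from 5.4.2: one-sided alpha 0.05, power 80%, medians 6 and 12 months (hazard ratio 0.5 if exponential), 36 months of accrual plus 12 of follow-up.

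- Events (Schoenfeld): 4 × (1.645 + 0.842)² / (ln 2)² = 51.5, so 52.
- Probability of an observed event: 0.941 on placebo and 0.790 on drug, mean 0.865.
- N = 52 / 0.865 = 60.1. Power at N = 60 (51.9 events) is 80.3%.

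The stated 60 reproduces. It is a patient-level calculation with one common hazard per arm.

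**2. Power with and without lesion count.** Simulation: 30 per arm, 20,000 trials per scenario (Monte Carlo error about 0.3 points), exact event times, one final test at one-sided 0.05, no dropout (none is stated). Patient hazard is proportional to count^a: a = 1 means independent lesions, a = 0.5 partial dependence, a = 0.25 weak dependence. The hazard ratio within each count is 0.5, and pooled medians are held at 6 and 12 months. The mixes of patients with 1/2/3 index lesions are assumptions. With every patient at one lesion, all three tests give 78.8%.

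| Mix 1/2/3 (%) | a | Unadjusted log-rank | Cox score, log count | Log-rank stratified by count | Cox minus unadjusted |
|---|---|---|---|---|---|
| 90/8/2 | 1 | 77.3 | 78.5 | 77.2 | 1.2 |
| 80/15/5 | 1 | 74.9 | 78.2 | 75.8 | 3.3 |
| 60/25/15 | 1 | 70.9 | 77.6 | 74.2 | 6.7 |
| 50/30/20 | 1 | 69.3 | 77.7 | 74.1 | 8.4 |
| equal thirds | 1 | 69.2 | 77.9 | 74.5 | 8.7 |
| 50/0/50 (extreme) | 1 | 65.4 | 77.4 | 75.8 | 12.0 |
| 80/15/5 | 0.5 | 78.5 | 79.3 | 76.5 | 0.8 |
| 60/25/15 | 0.5 | 77.3 | 78.7 | 75.4 | 1.4 |
| equal thirds | 0.5 | 76.4 | 78.3 | 74.7 | 1.9 |
| 50/0/50 (extreme) | 0.5 | 75.4 | 78.6 | 77.0 | 3.2 |
| 60/25/15 | 0.25 | 78.7 | 78.7 | 75.4 | 0.0 |
| equal thirds | 0.25 | 78.9 | 79.1 | 75.6 | 0.2 |

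A second set of mixes under independence, with 50-75% single-lesion patients, gave 69-73% unadjusted against 77-78% adjusted, a gap of 4 to 9 points. If count has no effect (a = 0), adjustment costs between under 0.5 and about 1 point. With no drug effect (a = 1, equal thirds), one-sided type I error was 5.5% unadjusted and 5.6% Cox-adjusted.

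**3. Chance imbalance.** Let D be the between-arm difference in number of multi-lesion patients, with 30 per arm and no stratification.

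- 40% multi-lesion: variance 2 × 30 × 0.4 × 0.6 = 14.4, SD 3.79. P(|D| ≥ 5) ≈ 2 × [1 − Φ(4.5/3.79)] = 24%.
- 25% multi-lesion: variance 2 × 30 × 0.25 × 0.75 = 11.25, SD 3.35. P(|D| ≥ 5) ≈ 18%.

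At 60/25/15, when an excess of five or more falls on drug, unadjusted power is 51% if lesions are independent and about 65% at a = 0.5. Cox adjustment holds about 77%. When the excess falls on placebo, unadjusted power rises to 84-87%.

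**4. Measurement error.** The reproducibility table in 1.2.8 gives median inter-day CVs of 3.6% (observer 1) and 1.6% (observer 2). For a lesion truly at +15%, with independent errors at both scans, P(reads ≥ 20%) = 1 − Φ[ln(1.20/1.15) / (√2 × CV)].

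- CV 3.6%: 1 − Φ(0.836) = 0.20; at least one of three, 1 − 0.80³ = 0.49.
- CV 1.6%: 1 − Φ(1.88) = 0.03; at least one of three, 1 − 0.97³ = 0.09.

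This is separate from the power figures, which use exact times.

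**The case against.** The planned test is conventional, and randomisation protects it. The 6 and 12 month medians are patient-level. If patient-level hazards are proportional with ratio 0.5, as the sample-size calculation implies, the log-rank keeps its 80% and adjustment is only a possible gain. That stands, and it is why this is a point about efficiency.

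A reader might settle on one figure, such as 6 to 8 points lost. The documents do not support that. It needs independent lesions and a mix with many multi-lesion patients, and the documents give neither. They lean against independence: 5.4.1 says most of these tumours outgrow the body in childhood and plateau by the end of puberty, an age effect shared by lesions in one patient. Nor is 8 a ceiling, since the extreme mix gives 12.

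A reader might also take the 49% as the trial's misclassification rate. It uses one observer's CV and puts all three lesions at exactly +15%; the other observer's CV gives 9%.

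Appendix 8A has no field for index-lesion count. That is true, but the lesions are identified before treatment (2.2.7, Appendix 1) and measured centrally (5.5.5), so the count exists at baseline.

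The paired comparison in 5.4.2 uses each patient as his or her own control, but it is additional and leaves the primary test unchanged.

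**Conclusion.** The point holds as one of efficiency and chance imbalance. Lesion count predicts event time through the endpoint rule, and the primary test ignores it. The cost is about 0 to 9 points of power: close to nothing under weak dependence, about 1 to 3 under partial dependence, and about 4 to 9 if lesions are independent and at least a quarter of patients have several (about 3 at 80/15/5). Only the extreme half-and-half mix goes beyond that range. All of this rests on assumed mixes and an assumed relation between count and hazard.

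It should not be read as bias: type I error is essentially the same with and without adjustment. Nor does it show that the sample size was miscalculated, since 60 reproduces. The exposure to imbalance is the stronger practical argument, because it matters even at a = 0.5, where the average gain is small.

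**What to change.** In 5.4.2, pre-specify before any unblinding a phase A Cox score test for treatment adjusted for log number of index lesions (1, 2 or 3), with the count taken from the central baseline MRI review. Keep the unadjusted log-rank as a sensitivity analysis, and report lesion-count balance by arm. The choice must come first, because an adjustment adopted after an imbalance has been seen is not credible.

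Two alternatives are not recommended. A log-rank stratified by count can lose about 1 to 3 points when count is only weakly or partly prognostic (for example 77.3% to 75.4% at 60/25/15, a = 0.5). Pre-study growth rate should be left out or kept exploratory: 2.1.1.3 admits 1D, 2D or volume change on MRI or CT, patients may enter on new lesions or after incomplete resection, and 1.2.8 describes growth as erratic.

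The cost is analysis wording and recording the count from central review, with no extra patients, scans or visits. The downsides are up to about 1 point of power if count is not prognostic, and that the three interim looks and the final O'Brien-Fleming evaluation must all use the same adjusted statistic.

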3.1.6 TISSUE PROCUREMENT

This study will attempt to obtain biopsies from easily accessible discrete neurofibromas or superficial plexiform neurofibromas from all eligible patients prior to the start of treatment, and if feasible at a later time point during treatment (at steady state, between day 15-21 on cycle 1) on each treatment phase. In addition, attempts will be made to obtain tumor specimens from any patients requiring surgery for complications of their tumors or for unrelated medical problems (Appendices 3 and 4). Peripheral blood mononuclear cells for FPTase activity (Section 3.1.8, Appendix 5) should be collected at the same time as the biopsy.

The following studies will be performed with tumor specimens (Appendices 2, 3, 4): (1) FPTase activity, (2) expression of N-ras, H-ras, and K-ras, and (3) ras mutations, and (4) NF1 mutations in the GAP related domain, (5) establishment of tumor cell lines, and (6) detailed immunohistochemical analysis (plexiform neurofibromas only). Findings will be correlated with response to treatment with R115777. It is hypothesized that ras mutations will be rare, germline NF1 mutations will be found in all tumors, and additional NF1 mutations will be found in many cases.

3.1.7 ESTABLISHMENT OF TUMOR CELL LINES AND TISSUE BANK

Attempts will be made to establish tumor cell lines from tumor specimens from patients treated on this trial. The tissue bank and pathology review will be open to use by the scientific community, provided IRB approval for research questions not addressed by this protocol is obtained, in order to collect more information on the pathology, genetics, and cell biology of plexiform neurofibromas.

3.1.8 FPTASE ACTIVITY IN PBMC

FPTase activity will be assessed in PBMCs pretreatment and once between days 15 and 21 of treatment (steady state) on cycle #1 of each treatment phase ("A" and "B") as a surrogate marker for the effect of R115777 (Appendix 5). PBMCs should be obtained at the same time as tumor biopsies in patients who consent to a biopsy.

